#### **5.4 Analysis of Secondary Endpoints**

**Comparison of ear canal volume (ECV), static admittance (SA) and tympanometric peak pressure (TPP):** The agreement in ECV, SA, and TPP between the commercial device and prototype device using Bland-Altman approach. The difference plot (plot of difference in measurement vs mean measurement) will be used to visualize the difference as well as to assess the assumption of normality for the differences. The limits of agreements (LoA) will be constructed: mean of difference  $\pm 1.96 \times \text{SD}$  of difference. It is expected that LoA will capture 95% of the differences in measurements between the two devices. The distributional assumptions related to Bland-Altman method will be validated (e.g. normality of difference will be tested for statistical significance using Shapiro-Wilk's test) and alternate approaches such as data transformation may be employed if needed. It is anticipated that the difference in ECV and TPP between the commercial device and prototype device will be within 0.4 and 40 measurement units respectively. The difference in distribution of the ECV, SA, and TPP will be assessed (separately) for statistical significance using Wilcoxon signed rank test.

**Comparison of ease of device usage:** The ease of device usage based on audiologist's assessment will be measured using a 4-question survey. Each survey question is presented on 5-point Likert scale (Completely Disagree, Disagree, Neither agree or disagree, Agree Completely, Agree). The response will be assigned a score of 1-5 (corresponding to Completely Disagree-Completely Agree) with higher score indicating greater

degree of agreement. For each audiologist an aggregated score will be obtained. The aggregated score will range from 4-20 with higher score suggesting greater ease of use. Each audiologist will contribute two assessments – one for the prototype device and the other for the commercial device. The difference in aggregated score between the two devices will be tested for statistical significance using Wilcoxon signed rank test.

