Analyses for the pilot validation will include: 1) comparison of categorical classifications of tympanogram types for the commercial vs prototype devices; 2) evaluating potential intra-participant correlation between ears; 3) assessing differences in numerical measures between the commercial and prototype tympanometer; and 4) evaluating performance of mHealth tympanometer and commercial tympanometer.

- 1) For each device, commercial and prototype, tympanograms will be categorized into one of 3 categories: A, B and C. To assess the agreement between the two devices with respect to categories, Bowker's test of symmetry and the Kappa coefficient conventional methods to assess agreement, will be used. For the initial analysis, both tympanograms will be performed for each ear and no adjustments will be made for participants (i.e., most will have both ears included).
- 2) To assess the potential effect of participant and ear status (normal, diseased) for participants where both ears are included, each participant's ears will be characterized as (both normal, both diseased, one diseased and one normal). Within those categories, the number of ears for which there is concordance between the two tympanograms for each participant will be 0, 1 or 2. Pearson's chi-square test will be used to compare the three groups defined by ear status with respect to the distributions of the number of ears with concordance.
- 3) The Wilcoxon signed rank test will be used to determine if the differences in the numerical measures (ear canal volume, static admittance and tympanometric peak pressure) obtained from the commercial and prototype devices are significantly different from zero. No adjustment for multiple testing is planned.
- 4) Audiologist assessment of the mHealth and commercial tympanometers will be captured through questionnaires which assess 4 performance measures using a 5-point Likert scale. For each performance measure, the Kappa coefficient and Bowker's test of symmetry will be used to assess agreement between the two mHealth and commercial tympanometers with respect to responses.

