A minimum of 30 participants will be enrolled. Both ears will be used for each patient enrolled, with enrollment remaining open until 60 ears (40 adult and 20 pediatric ears) are accrued to ensure that there are sufficient number of ears for analysis. It is possible that more than 30 participants will be required to accrue 60 ears if we are unable to obtain a tracing on one or both ears in certain patients (such as due to a draining ear, which inhibits formation of a seal). We anticipate consenting no more than 40 individuals to reach the enrollment goal of 30 participants. With a sample size of 30 participants (60 ears), a null hypothesis where kappa is 0 (no correlation between devices) can be tested against the alternative hypothesis of kappa of 0.3 using a two-sided 0.05 significance level with a power of 0.89.

Title: "Pilot Validation of a Prototype Mobile Health Tympanometer"
PI: [name], MPH
Institution: University of Arkansas for Medical Sciences

Machine Learning Algorithm Analysis

The categorizations of the tympanogram (Type A, B, C) classified by the algorithm will be compared with the audiologists' interpretations. To assess agreement between the audiologist and the algorithm, Kappa analysis and Bowker's test of symmetry will be performed.

Ethical Considerations

This study will be conducted in accordance with all applicable government regulations and UAMS research policies and procedures. This protocol and any amendments will be submitted and approved by the IRB as required.

For recruitment and eligibility determination, a partial HIPAA waiver will be obtained. PHI access under the partial HIPAA waiver will entail using the clinic schedule to screen for potential participants by their age and reason for visit. Reason for visit will be used to determine middle ear status and whether tympanometry is likely to be performed as part of the clinical visit.

For eligible participants and parents/guardian of eligible children, informed consent using IRB-approved consent materials, will be obtained before the participant begins any study procedures and will be performed electronically using a secure REDCap database. All participants for this study will be provided an electronic informed consent form (e-consent) describing this study in language understandable to the study population.

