### 2.2 Power and Sample size

A sample size of 30 participants (60 ears), with an assumed prevalence of 0.20 will yield a half-width of 95% confidence interval ranging from 0.25-0.33 when the sample sensitivity is 0.80; and a half-width of 95% confidence interval ranging from 0.12-0.18 when the sample specificity is 0.80. The range of the half-width of 95% confidence interval reflect the extreme scenario of the intra-class correlation ranging from 0 to 1.

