### 2.3 Sampling Strategy

Convenience sampling will be employed for this study. We will recruit a minimum of 30 participants, which will include adults (n=20) presenting to the Audiology Clinic of University of Arkansas for Medical

Sciences (UAMS) and pediatric participants (n=10) presenting to Arkansas Children's (AC) Audiology Clinic. In total, a minimum of 60 ears will be included in the analysis.

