### 4 Outcomes, Exposures, and Additional Variables of Interest

#### 4.1 *Outcome(s)*

Table 2. Description of outcome variables

Outcome	Description	Variables and Source	Specifications
Primary Outcome(s)			
Categorical classification of tympanogram types A, B, C  1) Audiologist's interpretation of commercial device versus audiologist's interpretation of prototype device  2A) Audiologist's interpretation of prototype device versus machine learning algorithm's interpretation of prototype device  2B) Audiologist's interpretation of commercial device versus machine learning algorithm's interpretation of prototype device	Tympanograms can be classified into types (Type A, B, C) that help to determine if an eardrum has fluid behind it, is retracted, or perhaps has a perforation, all common ear disease states. Type A indicates normal ear function, and types B and C indicate abnormal middle ear function.	Audiologist commercial device classification (left, right): Tymp_type_au_com_l; Tymp_type_au_com_r  Audiologist prototype device classification (left, right): Tymp_type_au_proto_l; Tymp_type_au_proto_r  Machine learning algorithm prototype device classification (left, right): Tymp_type_ml_proto_l; Tymp_type_ml_proto_r  Forms: 1) Data collection form: Audiologist interpretation and performance for mHealth tympanometer  2) Data collection form: Audiologist interpretation and performance for commercial tympanometer  3) ML Algorithm Interpretation form	1=A; 2=B; 3=C; 4=CNE (could not evaluate)
Secondary Outcome(s)			
Ear canal volume, static admittance and	Numerical measures	Commercial device (left, right):	Numerical measures

tympanometric peak pressure	Commercial device versus prototype device	
ecv_com_l; sa_com_l; tpp_com_l; ecv_com_r; sa_com_r; tpp_com_r
 
Prototype device (left, right): ecv_proto_l; sa_proto_l; tpp_proto_l; ecv_proto_r; sa_proto_r; tpp_proto_r
 
Forms: 1) Data collection form: Audiologist Interpretation and Performance for commercial tympanometer  2) ML Algorithm Interpretation form

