### **5.9 Missing data**

There could be missing values from either prototype or commercial device (e.g., Table 4, Ear 1, 2, 3 or Ear 5, 6) or both the devices (e.g., Ear 4). The analysis for all study objectives will be based on complete case analysis (the last column of Table 4 i.e., data available for both devices).

Missing data in the outcome variable arises from inability to take tympanometry measurements for a participant (CNE status), especially for children with the presence of ear pathology, or younger children less likely to sit still for measurements. We will not include an ear in the main analysis if data from one device

(either commercial or prototype) or both devices are missing for that ear. No multiple imputation is planned for this study.

The frequency and proportion of missing data will be presented separately for the prototype and the commercial device. Missing proportions will be compared for commercial and prototype devices by ear status, adults/children, number of ears and tested for statistical significance using either Chi-square test or Fisher's exact test.

Table 4: Example of missing values by device type

	Commercial device	Prototype device	Complete case analysis for all study objectives
Ear 1	✓	missing	
Ear 2	✓	missing	
Ear 3	✓	missing	
Ear 4	missing	missing	
Ear 5	missing	✓	
Ear 6	missing	✓	
Ear 7	✓	✓	✓
Ear 8	✓	✓	✓
Ear 9	✓	✓	✓
Ear 10	✓	✓	✓
...Ear 60			

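### The signed-rank tests of ECV, SA and TPP in SAP 5.4 make no allowance for two ears per participant

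*SAP*

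**What the plan says.** SAP 5.4 plans Bland-Altman limits of agreement for the three numerical measures and then a test: "The difference in distribution of the ECV, SA, and TPP will be assessed (separately) for statistical significance using Wilcoxon signed rank test". Item 3 of the protocol's Pilot Validation Analysis names the same test, to see whether the differences "obtained from the commercial and prototype devices are significantly different from zero". Neither place states the unit of analysis or mentions the pairing of ears within a person.

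The surrounding text points to the ear as the unit:

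- SAP 4.1, Table 2, stores left and right values separately, for example "ecv_com_l; sa_com_l; tpp_com_l; ecv_com_r; sa_com_r; tpp_com_r".
- SAP 5.9 applies complete-case analysis to all objectives and decides it ear by ear: "We will not include an ear in the main analysis if data from one device".
- SAP 2.3 sets the target in ears: "In total, a minimum of 60 ears will be included in the analysis". The protocol adds "We anticipate consenting no more than 40 individuals to reach the enrollment goal of 30 participants", so the 60 ears come from roughly 30 to 40 people.

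Item 1 of the protocol analysis says that "no adjustments will be made for participants (i.e., most will have both ears included", but this concerns the categorical comparison. Item 2 examines within-participant correlation only for concordance of categories. SAP 5.3 handles the clustering with GEE and a robust variance, Durkalski's test and a cluster bootstrap, but only for tympanogram types.

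**The concern.** The signed-rank test assumes independent differences. Two ears of one person need not give independent differences, and if they are positively correlated the test understates its variance and declares a device difference too often. Hypothesis 3 is worded as an absence of statistically significant differences, so on its literal wording this p-value decides it. A spurious difference would count against the prototype in a study whose results are meant to guide changes to the device. The error cannot produce a false claim of agreement and does not reach the primary endpoints.

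**Working it through.** **1. The plan's own allowance for clustering.** SAP 2.2 gives 95% half-widths whose ranges "reflect the extreme scenario of the intra-class correlation ranging from 0 to 1". With 60 ears and prevalence 0.20 there are 12 diseased and 48 normal ears at correlation 0, and the equivalent of 6 and 24 at correlation 1. Clopper-Pearson half-widths at 0.80 are 0.244 and 0.331 for sensitivity (stated 0.25 to 0.33), and 0.121 and 0.173 for specificity (stated 0.12 to 0.18). The stated figures are reproduced to within 0.01. For sensitivity and specificity, then, the SAP accepts that 60 ears may be worth as few as 30. For the Wilcoxon tests it states only the two-sided 0.05 of SAP 5.1.

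**2. Which correlation matters.** It is the correlation rho, between a person's two ears, of the difference prototype minus commercial. A person effect common to both devices cancels on subtraction, so correlated raw values alone do not show that rho is above zero. The documents give no value for rho, and it is varied below as an assumption.

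**3. Approximation.** Let s be the share of ears that come from two-ear participants.

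- Variance inflation: deff = 1 + rho × s
- Actual error of a nominal 5% test: 2 × (1 − Φ(1.96/√deff))

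With 30 participants × 2 ears, s = 1:

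- rho 0.3: deff 1.3, 1.96/1.140 = 1.72, error 8.6%
- rho 0.5: deff 1.5, 1.96/1.225 = 1.60, error 11.0%
- rho 1: deff 2, 1.96/1.414 = 1.39, error 16.6%

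With 40 participants (20 with two ears, 20 with one), s = 40/60 = 0.667:

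- rho 0.3: deff 1.2, error 7.4%
- rho 0.5: deff 1.33, error 9.0%
- rho 1: deff 1.67, error 12.9%

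**4. Simulation of the signed-rank test itself.** Normal differences, ears treated as independent, normal approximation, 40,000 runs per setting:

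| rho | 30 participants × 2 ears | 40 participants (20 two-ear, 20 one-ear) |
|---|---|---|
| −0.2 | 2.9% | 3.5% |
| 0 | 5.1% | 4.9% |
| 0.05 | 5.3% | 5.3% |
| 0.1 | 6.3% | 5.5% |
| 0.2 | 7.0% | 6.3% |
| 0.3 | 8.3% | 7.2% |
| 0.5 | 10.7% | 8.7% |
| 0.7 | 13.4% | 10.4% |
| 1.0 | 16.6% | 13.1% |

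An intermediate case of 35 participants (25 with two ears, 10 with one) gives 7.8% at 0.3 and 9.6% at 0.5. A repeat for 30 × 2 ears with normal and heavy-tailed (t with 3 degrees of freedom) differences gives 8.1% to 8.2% at 0.3 and 10.2% to 10.5% at 0.5, so the result does not depend on normality.

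**5. Tests that respect the participant.** A clustered signed-rank test (signed ranks summed within participant, variance equal to the sum of the squared participant sums) stays at 4.6% to 5.1% over these settings. A signed-rank test on participant means stays at 4.7% to 5.3%.

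**6. Limits of agreement.** For 30 × 2 ears, 30 of the 60 × 59/2 = 1,770 pairs of ears share a person. Hence E[s²]/σ² = 1 − rho × 30/1,770 = 1 − rho/59, where s² here is the sample variance of the differences. That is at most 1.7% low, so the point limits are essentially unaffected.

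**The case against.** SAP 5.4 never says that the 60 ears are treated as independent. A signed-rank test on participant means would fit its wording, and the table shells are in a separate document. That stands: ear-level analysis is an inference, though the natural one from the left and right variables, the ear-by-ear inclusion rule and the target in ears. An unstated unit is itself a gap, since two statisticians could follow 5.4 and report different p-values.

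The size rests on an assumed correlation. That also stands. Nothing in the documents favours 0.3 to 0.5 over 0 to 0.1, where the effect is small, and at a negative correlation the test is conservative. But both ears are measured at one visit in the same device order, so independence should not be taken for granted, and the proposed tests hold the error near 5% across the correlations tried.

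The practical effect is narrow. With 30 × 2 ears, the correct 5% threshold corresponds to a naive z of 1.96 × √1.3 = 2.23 (p about 0.025) at rho 0.3, or 1.96 × √1.5 = 2.40 (p about 0.016) at 0.5. Only naive p-values between those points and 0.05 change verdict. The three tests are also unadjusted for multiplicity by design; if independent, their family-wise error is already 1 − 0.95³ = 14%. These points keep the matter moderate, but they do not justify a wrong error rate for each test.

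SAP 1.1 permits justified deviations, but its reason is assumptions that can be checked only during analysis. Two ears per participant is known now.

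**Conclusion.** The concern holds. SAP 5.4 and protocol item 3 name an unadjusted signed-rank test for data that come mostly in pairs of ears, while SAP 5.3 allows for the same clustering in the primary analyses. If ears are analysed as independent and the device differences correlate 0.3 to 0.5 within a person, the nominal 5% error is about 7% to 11% over the 30 to 40 participants the protocol foresees, and about 8% to 11% if all 30 give both ears. It is close to nominal at 0.05, at most about 6% at 0.1, and 13% to 17% at the limit of 1. The omission is certain; the size depends on a correlation the documents do not give. The consequence is confined to a secondary endpoint and runs towards falsely rejecting Hypothesis 3. The change should be made, but nothing in the primary analysis depends on it.

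**What to change.** In SAP 5.4:

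- State that the unit is the ear, clustered within participant.
- Replace the test with a clustered signed-rank test (Rosner-Glynn-Lee) with participant as the cluster. A signed-rank test on each participant's mean difference over available ears is a simpler alternative, but it gives one-ear and two-ear participants equal weight.
- Leave the limits-of-agreement formula as it is. If an interval for the mean difference or for the limits is reported, obtain it by resampling participants.
- Add that a non-significant result is not evidence of agreement, and that agreement is judged from the limits of agreement.

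This takes a few lines of text and code and no new data.

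The statistical cost arises when the correlation is positive: p-values become larger, so the non-significant result that Hypothesis 3 favours becomes more likely. At an assumed true shift of 0.3 SD of the differences (20,000 simulations), the probability of non-significance changes as follows:

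| Participants | rho | Naive test | Clustered test |
|---|---|---|---|
| 30 | 0.3 | 39.7% | 50.9% |
| 30 | 0.5 | 40.8% | 55.8% |
| 40 | 0.3 | 40.6% | 48.4% |
| 40 | 0.5 | 40.7% | 51.5% |

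This is why the sentence on agreement belongs with the change. An interval for the mean difference is wider than a naive one by √deff, that is by 14% to 22% with 30 participants and 10% to 15% with 40, at correlations of 0.3 to 0.5.

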Eligible patients will be invited to participate, and the consent form reviewed. Consented participants will receive their audiological services as scheduled, with the addition of prototype measurements to their appointment. The audiology appointment will include routine ear and hearing measures, such as otoscopy (visual ear exam) and pure tone

Title: "Pilot Validation of a Prototype Mobile Health Tympanometer"
PI: [name], MPH
Institution: University of Arkansas for Medical Sciences

testing. The prototype device will be conducted before the commercial tympanometry. Audiologists will be asked to complete the prototype measurement and interpretation prior to the commercial device to limit bias in study results. We anticipate approximately 3 audiologists from UAMS and 2 audiologists from AC being involved in the study. Audiologists will be provided initial training and a demonstration of the prototype device and given instruction on how to troubleshoot and who to contact should an unanticipated problem occur. The tympanometric measurement takes roughly 10-15 seconds per ear to collect. We anticipate the prototype measurement and data entry will take no more than 5 minutes to complete during the audiological appointment.

The resulting tympanograms from the prototype device and the clinical tympanometer will be interpreted by the audiologist and entered in a secure Research Electronic Data Capture (REDCap) database. The audiologist will also answer a few brief questions during/after testing each participant in a REDCap form on device performance for both the prototype and commercial tympanometers.

Specifically, the order of events will be as follows:

1. Audiologist will test each ear of the participant with the prototype device and interpret the tympanogram. These findings will be entered in a secure Research Electronic Data Capture (REDCap) database in real time using a tablet or computer.
2. Next, the audiologist will test each ear of the participant with a commercial tympanometer, interpret the results and enter them in the database as described above.
3. The audiologist will complete 4 questions on each device performance between testing with each device (steps 1 and 2) if time permits, or after completion of testing with both the devices, and document it in a secure REDCap database.

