## 2 Study Methods

### 2.1 Study Design

Pilot Validation: This is a pilot validation study involving a comparative investigation of a commercially available tympanometer with a minimal risk lay-friendly (mHealth) tympanometer prototype. The pilot validation will be conducted in consented adults and children presenting to the Audiology Clinics of UAMS and AC. The study will evaluate device performance compared to a commercial tympanometer in patients with various middle ear pathologies. Data acquired from the pilot validation will also be used with our machine learning algorithm to determine how well it works with prototype data and the if there will be a need for further refinement.

Eligible patients will be invited to participate, and the consent form reviewed. Consented participants will receive their audiological services as scheduled, with the addition of prototype measurements to their appointment. The audiology appointment will include routine ear and hearing measures, such as otoscopy (visual ear exam) and pure tone testing. The prototype device will be conducted before the commercial tympanometry. Audiologists will be asked to complete the prototype measurement and interpretation prior to the commercial device to limit bias in study results.

The resulting tympanograms from the prototype device and the clinical tympanometer will be interpreted by the audiologist and entered in a secure Research Electronic Data Capture (REDCap) database. The audiologist will also answer a few brief questions after testing each participant in a REDCap form on device performance for both the prototype and commercial tympanometers.

Specifically, the order of events will be as follows:

1. Audiologist will test each ear of the participant with the prototype device and interpret the tympanogram. These findings will be entered in a secure Research Electronic Data Capture (REDCap) database in real time using a tablet or computer.
2. Next, the audiologist will test each ear of the participant with a commercial tympanometer, interpret the results and enter them in the database as described above.
3. Finally, the audiologist will complete 4 questions on user experience with the prototype and commercial devices and document it in a secure REDCap database.

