## 2.7 Data Acquisition

Table 1. Data acquisition

Study design	Pilot validation study
Data source/how the data were collected	
REDCap Survey: Link will be added later
 
Data collected during study visit:
 

• Enrollment form

• Data collection form

◦ Audiologist Otoscopy Interpretation

◦ Audiologist Interpretation and Performance for prototype device

◦ Audiologist Interpretation and Performance for commercial tympanometer

• ML Algorithm Interpretation form

Contact information for team member responsible for data collection/acquisition	
Date or version (if downloaded, provide date)	
Data transfer method and date	
Where dataset is stored	REDCap

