## 5 Analysis Plan

### 5.1 General Considerations

Analysis timeline: The final statistical analysis will be performed after study data is available from 30 participants (60 ears); and the Center for Hearing Health Equity data management team has completed the transfer of an analysis-ready dataset to the study statistician.

Statistical Software: The analysis will be done using SAS (version 9.4) and R (version 4.3.2). A two-sided alpha of 0.05 will be used to determine statistical significance.

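### SAP 5.4 tests ease of use on one score pair per audiologist, but the survey is collected per participant; no rule links the two units, and each leaves the planned signed-rank test with a problem

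*SAP*

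**What the plan says.** **Unit of analysis.** SAP 5.4 (Comparison of ease of device usage) states "For each audiologist an aggregated score will be obtained" and "Each audiologist will contribute two assessments", one for each device. The score runs from 4 to 20, and the difference between devices goes to a Wilcoxon signed-rank test. SAP 5.1 sets a two-sided alpha of 0.05 and names SAS and R, without saying whether p-values are exact or asymptotic.

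**Unit of collection.** The protocol (Study Design and Procedures) says "The audiologist will also answer a few brief questions during/after testing each participant in a REDCap form". SAP 2.1 agrees: "The audiologist will also answer a few brief questions after testing each participant". Step 3 of the SAP's order of events reads "Finally, the audiologist will complete 4 questions on user experience with the prototype and commercial devices"; it closes the sequence for one participant. SAP 2.7, Table 1, lists "Audiologist Interpretation and Performance for prototype device" among the data gathered at the study visit. SAP Table 2 puts the four survey items for each device on the same forms as the tympanogram types.

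**Numbers.** The protocol says "We anticipate approximately 3 audiologists from UAMS and 2 audiologists from AC being involved in the study". SAP 5.1 times the final analysis at 30 participants (60 ears).

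**Hypothesis and parallel plan.** Hypothesis 4 (SAP 1.3) predicts that ease of use will not differ significantly between devices. Protocol, Data Analysis, item 4, analyses the same survey item by item with Kappa and Bowker's test and states no unit.

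**The concern.** The form is filled in about 30 times per device, but SAP 5.4 expects about five scores per device. No section says whether an audiologist's repeated forms are averaged, whether one is selected, or whether each is analysed separately. The choice changes the number of pairs roughly sixfold.

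Each unit brings its own difficulty. With about five pairs, the planned test has almost no room to reach significance, and Hypothesis 4 counts non-significance as success. With about 30 pairs, the test treats repeated judgements by the same few people as independent. The SAP models clustering of ears within participants for the primary endpoints (5.3) but makes no provision for audiologist.

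At stake is the ease-of-use conclusion only: either an apparent confirmation that no data could have contradicted, or a significant result driven by the preferences of a few audiologists.

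**Working it through.** The documents give no power, effect size or sample size for this endpoint, so there is no planned figure to reproduce.

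**Inputs from the documents:** approximately 3 + 2 = 5 audiologists (protocol); 30 participants and two-sided alpha 0.05 (SAP 5.1); score 4–20 (SAP 5.4).

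**Step 1: what the score range settles.** Four items scored 1–5 give 4 to 20, which is one completed form. At 30/5 = 6 participants per audiologist, a plain sum over forms would run from 6 × 4 = 24 to 6 × 20 = 120. The stated range therefore excludes a sum over forms. It fits an average, a single selected form, or one pair per participant.

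**Step 2: audiologist as unit.** The smallest exact two-sided signed-rank p-value with n untied, non-zero differences occurs when all have the same sign: 2/2^n.

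| Audiologists | Smallest exact p |
|---|---|
| 4 | 0.125 |
| 5 | 0.0625 |
| 6 | 0.031 |

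With five, no result reaches 0.05. With six, all six must agree.

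The normal approximation behaves differently. For n = 5 with all differences positive, the rank sum is 15 and its null mean is 5 × 6/4 = 7.5.
- Without ties the variance is 5 × 6 × 11/24 = 13.75 (SD 3.708). Then z = 7.5/3.708 gives p = 0.043, or z = 7.0/3.708 with continuity correction gives p = 0.059.
- With all five differences equal, every rank is 3 and the variance is 5 × 3²/4 = 11.25 (SD 3.354). Then p = 0.025, or 0.037 with correction.

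| Five differences | p, corrected | p, uncorrected | Exact p |
|---|---|---|---|
| 1,2,3,4,5 | 0.059 | 0.043 | 0.0625 |
| 1,1,2,2,3 | 0.057 | 0.041 | 0.0625 |
| 1,1,1,2,2 | 0.053 | 0.038 | 0.0625 |
| 2,2,2,2,3 | 0.048 | 0.034 | 0.0625 |
| 2,2,2,2,2 | 0.037 | 0.025 | 0.0625 |

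R's default routine returns 0.0625 for the first row and 0.037 for the last, because it switches to the approximation when there are ties. Ties are likely on a short integer scale. The verdict on the same unanimous preference can thus turn on a computing option that the SAP does not set.

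**Step 3: participant-level form as unit.** An audiologist's general leniency cancels in the prototype-minus-commercial difference; a personal preference for one device does not. Type I error of the unadjusted signed-rank test was simulated with 10,000 runs per cell and no true mean difference.

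Assumptions, none from the documents: integer totals limited to 4–20, mean 14, SD of the difference 2 before rounding, tie and continuity corrections, and the ICC of the differences as shown. Two workloads were used: 6 pairs for each of 5 audiologists, and 7,7,6,5,5 (20 adults over 3 audiologists, 10 children over 2). Each cell gives leniency SD 0 / SD 2.

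| ICC | Equal load | 7,7,6,5,5 |
|---|---|---|
| 0 | 0.048 / 0.043 | 0.051 / 0.050 |
| 0.1 | 0.095 / 0.101 | 0.105 / 0.102 |
| 0.2 | 0.151 / 0.147 | 0.163 / 0.153 |
| 0.3 | 0.204 / 0.208 | 0.213 / 0.205 |
| 0.5 | 0.297 / 0.289 | 0.291 / 0.300 |

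The design effect 1 + (6 − 1) × ICC points the same way: 1.5 at ICC 0.1 and 2.5 at 0.3, so 30 pairs carry the information of about 30/1.5 = 20 and 30/2.5 = 12 independent ones.

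**The case against.** The best defence is that the aggregated score simply means the sum of four items on one form. The range 4–20, the visit-level forms and the single set of variables per device all fit that, and then no rule for combining forms is needed. This has force and is the reading that the fix adopts. It does not remove the problem, because the sentence "Each audiologist will contribute two assessments" says otherwise, and it leaves the audiologist clustering unaddressed.

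A reader might infer that neither unit can support a signed-rank test at all. The documents do not take one that far:
- The headcount of five is approximate, and with six an exact p of 0.031 is attainable. An exact test at five is valid but cannot reject.
- At participant level the test holds its level when the ICC is 0. All the inflation comes from assumed ICCs.
- The inflation also presumes inference to audiologists beyond those taking part. Objective 4 speaks of audiologists' perceptions without claiming a wider population. If only the participating audiologists are the target, a consistent preference among them is a real difference, not a false positive.

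Nor do the documents justify ruling out every confidence interval; that would be a matter of preference.

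SAP 1.1 allows justified deviations, and the table shells are in a separate document not available here, which may show the unit. Neither supplies the rule in the plan's text, and the unit of analysis can be settled before any data are seen.

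**Conclusion.** The plan contradicts itself on the unit for the ease-of-use analysis: one pair for each of approximately 5 audiologists in SAP 5.4, against about 30 participant-level pairs under the collection procedures, with no linking rule.

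Followed literally with five audiologists and an exact test, SAP 5.4 can never reject, so Hypothesis 4 would look confirmed whatever the data. A normal approximation gives 0.037–0.059 (corrected) or 0.025–0.043 (uncorrected) when all five agree. These statements depend on the headcount staying at about five.

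With the participant-level pair as the unit, type I error is 0.043–0.051 at ICC 0 and about 0.10, 0.15–0.16, 0.20–0.21 and 0.29–0.30 at ICCs of 0.1, 0.2, 0.3 and 0.5. That holds only for conclusions about a wider population of audiologists and for correlations that are assumed.

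Under either unit, a non-significant result is not evidence that the devices are equally easy to use, since Hypothesis 4 sets no margin.

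Severity is minor. The endpoint is secondary in a pilot, and the primary analyses are unaffected.

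**What to change.** - **Unit.** In SAP 5.4, replace the two per-audiologist sentences. State that the unit is the participant-level survey pair: prototype and commercial forms from the same audiologist for the same participant, each totalling 4–20.
- **Main result.** Report the paired prototype-minus-commercial differences overall and by audiologist, with the number of pairs from each.
- **Testing.** Do not let the unadjusted Wilcoxon p-value decide Hypothesis 4. Any test or interval that is kept should be labelled exploratory, should account for audiologist, and should carry the caution that about five clusters is few.
- **Hypothesis.** In SAP 1.3, reword Hypothesis 4 as a descriptive objective.
- **Consistency.** Reconcile SAP 5.4 with the item-level Kappa and Bowker plan in the protocol (Data Analysis, item 4).

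**Cost.** No new data; wording changes in SAP 1.3 and 5.4. If protocol item 4 is changed, that is an amendment needing IRB submission and approval. The price is that this secondary endpoint has no confirmatory p-value.
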